18.2.1 Primary Endpoint

• 28-day survival

18.2.2 Secondary Endpoints

- 58 day survival time
- Change in Ebola virus threshold cycle within first 72 hours after randomization
- Rate of Ebola viral clearance, quantified as change in threshold cycle per day
- Time from randomization to first negative Ebola PCR
- Cumulative incidence of serious adverse events (SAEs)
- Cumulative incidence of adverse events (AEs) as assessed by laboratory monitoring
- Incidence of infusion related adverse reactions
- Frequency of clinically significant study agent administration or infusion reactions
- Duration from time of symptom onset to discharge from treatment unit or hospital
- Cumulative incidence of progression to severe disease (hemorrhage, multi-organ failure, seizures)
- Cumulative incidence from the time of randomization to resolution of gastrointestinal symptoms (vomiting and diarrhea).

- Cumulative incidence from time of randomization to resolution/progression of individual clinical symptoms
- Maximal serum creatinine in first 14 days
- Pharmacokinetics of investigational therapeutics
- Long term follow-up, when feasible, for any late onset clinical history or symptoms possibly consistent with delayed virologic relapse.

Overview of Study Drugs

By the fall of 2014 preclinical studies, and/or past use of interventions with anecdotal evidence, had identified a number of lead candidate therapeutic interventions that might be considered as prime candidates for further study in patients with known Ebola infection. With time it was thought possible that additional antiviral or immune-enhancing agents with preclinical supporting data may be identified and added to this list. Conversely, emerging toxicity data, failure to replicate previous supportive findings in additional preclinical animal model testing, emerging data from other recent therapeutic trials in West Africa, or similarly negative factors conceivably could also lead to narrowing of this list over time. Further, if inclusion were to be expanded to patients with high-risk exposures but no documented infection, the list of putative MCMs could be broadened even further and would likely include putative vaccine candidates. However, confining this proposed RCT to just enrollees with documented infection, the likely lead candidates initially identified for consideration of study included:

- Convalescent or post-immunization plasma harvested from recent Ebola infection survivors:
 - In time it is possible that this category could potentially be expanded to include plasma donors who have participated in phase 1 anti-Ebola vaccine testing and whose plasma shows high neutralizing activity against the virus in animal or *in vitro* assays.
- ZMappTM triple monoclonal antibody cocktail from Mapp Biopharmaceutical:
 - A combination of 3 different humanized monoclonal antibodies against the Ebola glycoprotein.
- Tekmira siRNA (or "TKM-Ebola") from Tekmira Pharmaceuticals Corp:
 - A combination of small interfering RNAs targeting 2 of the 7 proteins in Ebola: Zaire Ebola L polymerase and Zaire Ebola polymerase complex protein (VP35), formulated with Tekmira's lipid nanoparticle technology. Targeting of the initial product was subsequently optimized against the prevalent Guinea strain of the 2014 virus.
- Favipiravir from Toyama Chemical Co., LTD:
 - A selective inhibitor of RNA-dependent RNA polymerase with activity against a wide variety of viruses.
- BCX4433 from BioCryst
 - viral RNA-dependent RNA polymerase (RdRp) inhibitor
- AVI-7537 from Sarepta
 - o phosphorodiamidate morpholino oligomer

This list was not intended to be exhaustive, and future inclusion of other drug candidates (e.g. different monoclonal antibody cocktails targeted at epitopes identical to those in ZMappTM) was not prohibited by these examples.

Considerations in Choice of Study Drugs

Several factors influencing choice and sequence of study drugs/interventions to be compared in this protocol must be considered:

- Willingness of both the pharmaceutical sponsors and the FDA to allow each of these drugs to be studied according to this proposed trial design
- Sufficient and dedicated supply of individual agents to allow them to be available for study over the projected timeline of the trial
- Ongoing equipoise of the investigators that
 - No available individual agent has yet been demonstrated to be superior to oSOC
 - No available individual agent has yet been demonstrated to be superior to other agents
- No compelling safety/toxicity concern has emerged with respect to individual agents to favor their removal from consideration as study interventions
- The status of eIND access to these interventions during the projected timeline of this trial that may preclude, or circumvent, interest in enrollment of patients into this RCT.

With these considerations in mind, the starting choice of interventions to be entered into and compared in this trial was determined by a consensus of the site investigators performing this study at their individual treatment centers. The most recent deliberations of this group are reflected in Appendix A of this protocol.

Definitions for the Purpose of this Study

Enrolled

For the purpose of collecting data and samples, and reporting SAEs, a subject will be considered enrolled beginning from when the informed consent form is signed until the subject is considered either "discontinued", or "completed".

Discontinued

Subjects are considered discontinued when they meet 1 or more of the following criteria:

- Subject withdraws consent after being dosed and prior to the completion of Day 28 (see Section 19.5)
- Subject is withdrawn after enrollment by investigator (see Section 19.6) including lost to follow-up

Completed

Subjects are considered completed for the main study endpoint when they are followed through Study Day 58 (i.e. 30 days past the primary endpoint measured at Day 28) and complete the final study follow-up visit scheduled for that time. Patients willing to undergo extended follow-up for one year or more (i.e. to determine the incidence of any late onset history or symptoms potentially c/w virologic relapse) will still be considered as having

completed the study if a) they decline this extended follow-up, or 2) choose to discontinue extended follow-up prior to reaching one year past Day 58.

19 STUDY POPULATION

Research Subject Recruitment

Persons with confirmed Ebola virus infection at participating health centers may participate in the trial so long as the site can provide enhanced supportive care including the provision of fluid resuscitation (preferably intravenously, but potentially orally through nasogastric tubes), hemodynamic monitoring, and laboratory monitoring of fluid and electrolyte disturbances coupled with the ability to correct such abnormalities as they are detected.

19.1.1 Participation of Site Employees

Site employees who meet inclusion criteria may participate in this study, with the following conditions:

• Neither participation nor refusal to participate in this protocol will have any effect on the subject's subsequent employment or work situation.

Inclusion Criteria

- Males or females with documented positive PCR for Ebola virus infection within 10 days of enrollment
- Willingness of study participant to accept randomization to any assigned treatment arm
- Access to oSOC
- All males and females of childbearing potential, must be willing to use highly effective methods of contraception [e.g. absolute abstinence from potentially reproductive sexual activity, hormonal, surgical or multiple barrier/combined], from time of enrollment for the duration of study participation.
- Must agree not to enroll in another study of an investigational agent prior to completion of last required protocol visit (Day 58)
- Ability to provide informed consent personally, or by a legally-authorized [per applicable local laws and regulations] representative [LAR] if the patient is unable to do so.

Exclusion Criteria

- Any medical condition that, in the opinion of the site investigator, would place the patient at an unreasonably increased risk through participation in this study, including any past or concurrent conditions that would preclude randomization to one or more of the assigned treatment arms.
- Prior treatment with any investigational antiviral drug therapy against Ebola infection, other than experimental vaccines, within 5 half-lives or 30 days, whichever is longer, prior to enrollment.

Vulnerable Populations

19.4.1 Pregnant Women

A full understanding of the potential risks from the study medications to human fetuses is lacking at this time. However, given the mortality associated with Ebola virus infection and the likelihood that there is a greater risk to the fetus from severe infection than from the study medications themselves, pregnant women will be permitted entry into the study. However, there may still be certain study medications (e.g., favipiravir) with known teratogenic potential to which pregnant women should not be assigned, and these considerations must be reviewed on a case-by-case basis with study investigators. For example, if favipiravir happens to be the drug currently under study, pregnant women should not be enrolled in the trial during the period this particular drug is being tested.

The risks from the study medications to nursing infants are also unknown at this time. As women infected with Ebola will be quarantined in the Ebola Treatment Unit (ETU), breastfeeding will not be allowed.

For women who are pregnant, every attempt will be made to track the pregnancy outcome through delivery in order to determine the outcome of the study intervention on the fetus.

19.4.2 Inclusion of Children

Similarly, the study medications have only been tested in limited fashion, or not at all, in children. Again, however, children of any age will be eligible for enrollment given the likelihood that untreated Ebola infection may pose greater risk than study participation.

Subject Withdrawal

Subjects can terminate full or partial study participation at any time without prejudice. If a subject terminates participation before completing the study, the reason for this decision will be recorded in the study record. Persons voluntarily withdrawing may elect to allow continued collection of outcome information.

Best efforts will be made to follow withdrawn subjects who have received study interventions for safety.

Discontinuation of Subject by Investigator

The investigator has the right to withdraw subjects from the study. Subjects may be withdrawn from the study for any of the following reasons:

• The investigator believes that continuation in the study would be detrimental to the subject. In general, subjects withdrawn for AEs will still be followed for safety follow-up, if possible, as well as for ascertainment of the Day 28 mortality endpoint. If in the investigator's best judgment discontinuation is in the subject's best interest.

The reason for withdrawal from the study is to be recorded in the study record. If an SAE is unresolved at the time of discontinuation, efforts should be made to follow up until the event resolves or stabilizes.

Discontinuation of Study

The National Institute of Allergy and Infectious Diseases (NIAID), each institution's Institutional Review Board (IRB), or the Food and Drug Administration (FDA) may terminate this study at any time. Reasons for terminating the study may include, but are not limited to, the following:

- The incidence or severity of an SAE in this or other studies indicates a potential health hazard to subjects
- Subject enrollment is unsatisfactory
- Data recording is inaccurate or incomplete
- Investigators do not adhere to the protocol or applicable regulatory guidelines in conducting the study

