The trial primary endpoint is mortality by 28 days. The high mortality rate of Ebola virus disease and the uncertainty associated with the oSOC efficacy, mandate aggressive interim monitoring, which is described in the next section. If more than 2 treatment strategies are evaluated, the design will follow the same stopping rules outlined below, but randomization will proceed with equal probability to each of the arms. Strict control of the type I error rate would require adjustment of boundaries for comparison of multiple arms. We recommend against such adjustments, given the exigent circumstances surrounding the Ebola epidemic. Intention-totreat analyses will be employed. Each patient will undergo only a single randomization in the study.

Interim Monitoring

Methods of monitoring clinical trials generally require knowledge of the total amount of information at trial's end. Boundaries are then constructed to guide decisions to control the probability of falsely declaring a treatment benefit at one or more interim analyses, including the final analysis. Such boundaries correspond to scenarios in which the level of evidence in support of treatment efficacy (or the lack thereof) exceeds some pre-determined threshold. Early boundaries are usually very difficult to cross, while boundaries at the end of the trial are similar to what they would be in the absence of monitoring. Our setting requires a somewhat different paradigm because although the target sample size is 100/arm, circumstances beyond our control may lead to a smaller number of patients. Moreover, we would like the flexibility of modifying the oSOC arm quite early if results show the superiority of an experimental agent plus oSOC, for example. We recommend monitoring beginning with 6 participants in an experimental arm and 6 in the best supportive care arm, and continuing after every additional

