		4.5.5	Infusion Interruptions							
		4.5.6	Unanticipated problems							
5	DAI	LY STU	JDY PROGRESS REPORTS ON THE WEB	10						
6	SAE	E REPOI	RTS TO LEAFBIO	10						
7	SHE	ELLS FC	OR TABLES AND FIGURES	10						

31 1 STUDY OVERVIEW

The study protocol serves as the master protocol for the evaluation of multiple candidate countermeasures for the treatment of Ebola virus disease (EVD). The initial phase of the trial will focus on the evaluation of ZMapp and the order of additional treatments to be evaluated is still to be determined.

Participants in the initial phase will be randomized in a 1:1 allocation ratio to optimized standard of care (oSOC) or oSOC plus ZMapp. A maximum of 200 subjects will be randomized (100 per treatment arm) but frequent interim monitoring will be used to allow termination of the trial if a definitive result is achieved early in the trial.

The primary objective of this trial is to establish the safety and efficacy of investigational therapeutics in patients with Ebola virus infection. The primary endpoint for this trial is 28-day survival. Other key efficacy endpoints include: overall survival and time-to-viral load clearance. Safety endpoints

32 2 SUMMARY OF REPORTS

Table A3.1. Type of reports and their distribution

	Prepared			Distributed to			
Reports	by*	Distribution	Frequency [†]	Protocol co-chairs, blinded biostatisticians	DSMB	LeafBio	
Open Report to the DSMB	S	Electronic [‡]	М	X	X	Х	
Closed Report to the DSMB	S	Electronic [‡]	М		X		
Study Progress Reports	S, DM	Web site	Updated daily	X		Х	
SAE Reports							
By trt group	S	DSMB report	М		X		
Pooled **	S	Email	Upon request	X			
SAEs related to treatment	S, SO	Electronic	Event-driven		X	Х	
Safety Reports	S, SO	Electronic	Event-driven	X	X	X	

* Prepared by: DM = data manager, S = Independent biostatisticians,

SO = Safety office at the Statistical and Data Management Center (SDSMB), blinded to study arm

[†] Frequency: M = Prior to each DSMB meeting

[‡]Reports to the DSMB will be available for download from a secure server; upon request, DSMB members will also receive a hard copy. The open report will be posted on the study web site after the DSMB meeting.

** Reports are blinded to study arm assignment. All information will also be provided to the DSMB as part of the closed reports, by treatment group.

Abbreviations: SAE = serious adverse event

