4.4 Primary Outcome

The primary endpoint for this trial is 28-day mortality. All comparisons between treatment groups will follow the intent-to-treat principle, unless otherwise noted.

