3.8 Primary Outcome

The primary outcome is death within 28 days from randomization, and the primary population includes all randomized patients, with the exception of one individual who fled from the ETU on the first day and for whom no other primary data were subsequently captured.

Note: as a sensitivity analysis to assess the impact of the single subject with unknown vital status following randomization, the primary analysis described below will be performed assuming the subject was alive at 28 days and repeated assuming the subject was dead at 28 days.

Primary analysis

Inference relating to the primary endpoint will quantify the probability that the 28-day mortality rate is lower (or higher) under ZMapp relative to oSOC using the Bayesian paradigm as follows:

- A. The prior distribution of 28-day mortality probabilities, p₀ and p₁, in the oSOC and ZMapp arms is that of independent uniforms on [0,1].
- B. The posterior distributions of p₀ and p₁ after observing x₀ and x₁ deaths among n₀ and n₁ people in the two arms is that of independent betas with respective parameters (x₀+1, n₀-x₀+1) and (x₁+1, n₁-x₁+1).
- C. The posterior probability that p₁<p₀ will be computed: if this probability is 0.975 or greater, ZMapp will be declared superior to oSOC, whereas if the probability is 0.025 or less, ZMapp will be declared inferior to oSOC.
- D. Treatment effect estimates and 95% credible intervals will be computed for both the relative risk p_1/p_0 and absolute risk difference p_1-p_0 . The medians of the posterior distributions of p_1/p_0 and p_1-p_0 are used to estimate these quantities. 95% credible intervals are computed as follows.
 - a. For p_1/p_0 , compute lower and upper limits (L and U, respectively) satisfying $P(p_1/p_0 \le L \text{ given } x_0, x_1) = 0.025$ and $P(p_1/p_0 \ge U \text{ given } x_0, x_1) = 0.025$.
 - b. For p₁-p₀, compute lower and upper limits (L and U, respectively) satisfying P(p₁-p₀<L given x₀,x₁)=0.025 and P(p₁-p₀>U given x₀,x₁)=0.025.

Additional Supportive Analyses Using Primary Outcome:

Alternative test statistics:

The following alternative test statistics will be performed on the primary outcome as secondary analyses.

- Barnard's unconditional test will be performed using a one-tailed test of p₁=p₀ versus p₁<p₀.
 - A. The first alpha level used is 0.025 (one-sided). As with the Bayesian analysis, the overall type 1 error rate including monitoring may exceed 0.025.

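### After withdrawal, follow-up duties depend on dosing or on an AE reason, so Day 28 vital status is not required for every randomised patient

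*Combined protocol and SAP*

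**What the plan says.** The current protocol (sections 16 to 29) makes Day 28 death the primary endpoint: "The trial primary endpoint is mortality by 28 days" (section 22, Design). The Data Analysis Plan, section 4.4, adds: "All comparisons between treatment groups will follow the intent-to-treat principle, unless otherwise noted". Patients are "randomized in a 1:1 allocation ratio to optimized standard of care (oSOC) or oSOC plus ZMapp" (Data Analysis Plan, Study Overview), and section 20 makes the trial open-label.

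Follow-up after withdrawal is governed by these texts:

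- **Section 19, Subject Withdrawal.** A patient who leaves voluntarily can agree to further outcome collection, in either arm. The active duty on the site is the next one: "Best efforts will be made to follow withdrawn subjects who have received study interventions for safety".
- **Section 19, Discontinuation of Subject by Investigator.** Patients withdrawn for AEs are in general followed for safety where possible, "as well as for ascertainment of the Day 28 mortality endpoint". Withdrawal because the investigator judges it best for the patient has no matching rule. Unresolved SAEs are pursued in either arm.
- **Section 18, Definitions.** "For the purpose of collecting data and samples, and reporting SAEs, a subject will be considered enrolled" from consent until discontinued or completed. One route to discontinued is: "Subject withdraws consent after being dosed and prior to the completion of Day 28". The other is withdrawal by the investigator, which includes loss to follow-up.
- **Section 21.5.4.2.** Sites are to make every effort at the Day 28 visit. Withdrawn patients are not mentioned.

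**The concern.** An intention-to-treat mortality comparison needs vital status on everyone randomised, sought equally hard in both arms. Here the active duty after voluntary withdrawal turns on exposure. A control patient receives no investigational agent. A ZMapp patient can also leave undosed, since section 21.4.4 allows dosing to slip to Day 1.

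The definition of Discontinued points the opposite way. Read literally, a dosed patient who withdraws consent stops being enrolled for data and SAE collection, while an undosed one does not meet that criterion. Section 19 promises to follow the very patients for whom section 18 ends collection.

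The analysis gives this a route to the result. The Final Data Analysis Plan, section 3.8, takes all randomised patients "with the exception of one individual who fled from the ETU on the first day" and with no later primary data. If outcomes were lost unevenly by arm and left out in the same way, the loss would feed into the posterior probability that decides superiority.

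**Working it through.** **1. Who is covered for Day 28 vital status after withdrawal**

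| Route out | Dosed | Not dosed (all controls; ZMapp before dose 1) |
|---|---|---|
| Voluntary | Best efforts, for safety; outcome if the patient agrees | Outcome if the patient agrees |
| Investigator, AE | Day 28 mortality named | Day 28 mortality named |
| Investigator, other reason | Best efforts, for safety; no Day 28 rule | No Day 28 rule |

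No row gives an unconditional duty across arms except the AE row.

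**2. Reproducing the plan's figures**

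Inputs: uniform priors; looks at 6 to 20 per arm after each added patient, then at 40, 60, 80 and 100; thresholds 0.999 interim and 0.975 final in either direction (section 22). Exact recursion over the joint death counts gives power 0.879 for 0.20 vs 0.40 and 0.834 for 0.30 vs 0.50 (Table 11: 0.88 and 0.83). The null crossing probability at mortality 0.5 is 0.0637 (Table 11: 0.063). The decision rule is therefore understood correctly.

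**3. Effect of control-only loss**

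The documents give no withdrawal or loss rate, so the loss is an assumption. Mortality is 0.4 in both arms, with n randomised per arm and k controls lost. X0 (control) and X1 (ZMapp) are independent Bin(n, 0.4).

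- Lost patients survived: observed control data are X0 deaths of n − k.
- Lost patients died: observed control data are X0 − k deaths of n − k.
- The posteriors are independent Beta(deaths + 1, survivors + 1). Superiority is declared if P(p1 < p0) ≥ 0.975, and inferiority if it is ≤ 0.025 (Final Data Analysis Plan, section 3.8).
- The error rate is the sum of P(X0)·P(X1) over outcomes meeting the rule.

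At n = 100, expected observed control mortality moves from 40% to 40/95 = 42.1% or 40/90 = 44.4% if survivors are lost. It moves to 35/95 = 36.8% or 30/90 = 33.3% if deaths are lost.

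| n per arm | k lost | False superiority, survivors lost | False inferiority, deaths lost |
|---|---|---|---|
| 100 | 0 | 2.6% | 2.6% |
| 100 | 5 | 4.8% | 6.9% |
| 100 | 10 | 9.2% | 16.7% |
| 36 | 0 | 2.2% | 2.2% |
| 36 | 2 | 3.6% | 5.4% |
| 36 | 4 | 6.0% | 10.4% |

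With deaths lost at n = 100, false superiority falls to 0.9% (k = 5) and 0.2% (k = 10). If instead 2 survivors are lost in each arm at n = 36, it is 2.5%, close to no loss.

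The full sequential rule gives the same pattern at 5% and 10% control loss, with 100 observed per arm. False superiority goes from 2.9% to 5.5% and 10.3% (survivors lost); false inferiority goes from 2.9% to 7.1% and 16.6% (deaths lost).

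**4. Would the completeness check catch it?**

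Data Analysis Plan section 4.2 compares Day 28 form availability between arms by Fisher's exact test. For 5/100 vs 0/100 missing, two-sided p = 2·C(100,5)/C(200,5) = 0.059. For 4/36 vs 0/36, p = 2·C(36,4)/C(72,4) = 0.11. For 10/100 vs 0/100 the same formula gives 0.0015. The test finds gross imbalance but can miss amounts that matter.

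**5. Realised size**

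One of 72 outcomes is missing (1.4%). Suppose that patient was a control and the arms were 36 and 36; both are assumptions. Then setting the outcome to alive or dead changes the superiority decision with probability 0.013 when both mortalities are 0.4, 0.096 at 0.4 vs 0.2, and 0.089 at 0.5 vs 0.3.

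**The case against.** Much of the protocol is neutral between arms. The sentence just before the best-efforts one lets any voluntary leaver agree to outcome collection. The AE and unresolved-SAE rules have no arm condition, and AEs need not be drug-related, so controls qualify. Section 21.5.4.2 asks for full effort at Day 28, and section 21 (Site-Specific Considerations) relaxes data collection only where sites still obtain what the primary endpoint needs. The best-efforts sentence concerns safety, and extra safety follow-up of exposed patients is not in itself wrong. The term for what was received is also undefined: the synopsis speaks of an intervention in either arm, although sections 21.4.4 and 23.1.1 use it for investigational agents, so excluding controls is the likelier reading but not a stated one.

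A reader might infer that withdrawn controls are simply not followed. These texts do not support that. A reader might also infer that the bias favours ZMapp. Nothing in the documents says that those who leave are survivors, and the two dosing conditions pull in opposite directions.

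There are safeguards as well: the completeness comparison, withdrawal of consent reported by arm (Final Data Analysis Plan, section 3.5), sensitivity analyses for missing Day 28 mortality (section 22, Analyses), and the alive/dead reanalysis of the one missing patient (section 3.8).

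What stands after this: a patient's option to agree is not a duty on the site to ask. The general Day 28 effort does not say whether it reaches withdrawn patients. The safeguards reveal missing outcomes but cannot recover them, and the Final Data Analysis Plan's completeness section does not repeat the Fisher test.

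**Conclusion.** The concern holds as a gap and an inconsistency in the protocol. No sentence requires Day 28 vital status for every withdrawn patient whatever the arm, dosing or reason, and sections 18 and 19 conflict on dosed patients who withdraw consent. This permits arm-dependent ascertainment; it does not show that any occurred.

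The error rates in the working are conditional on loss confined to controls, and on all those lost having the same outcome, at 40% mortality. They are bounds for those scenarios, not forecasts, and loss balanced between arms largely removes the effect.

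The single missing patient should not be read as evidence that the rule caused harm. That patient left the unit on the first day, the arm is not stated, the documents do not connect the loss to any withdrawal rule, and the planned sensitivity analysis deals with it. The point matters mainly for further enrolment, which the Final Data Analysis Plan leaves open, and for any later stage of the master protocol.

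**What to change.** In section 19, state that for every randomised patient, whatever the arm, dosing or reason for withdrawal, Day 28 and Day 58 vital status and SAEs will be sought with the same contact effort unless the patient refuses. In section 18, delete the dosing condition from the consent-withdrawal criterion for Discontinued, and say that discontinuation does not end vital-status or SAE collection. This also removes the conflict between the two sections.

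The cost is a few sentences of protocol text, possibly one line in the consent form, and a few extra contacts for patients who withdraw.
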